### 7.1.2 Primary Efficacy Analysis

The primary analysis, which is event-based, will be conducted after enrollment is completed and approximately 250 IRC events have been observed in the study. A summary of PFS events will be provided by treatment arm.

The estimate of the hazard ratio (acalabrutinib/ibrutinib) and its corresponding 95% CI will be computed using a Cox Proportional Hazards model stratified by the randomization stratification factors (collapsed if necessary, according to Section 7). Randomization stratification factors will be based on IWRS randomization assignment.

If the upper bound of the 2-sided 95% CI for the HR is below 1.429, acalabrutinib will be concluded to be non-inferior to ibrutinib.

Kaplan-Meier (KM) curves will be presented by treatment arm and the KM method will be used to estimate the distribution of PFS (quartiles and median with 95% CIs, minimum, and maximum). The proportion of subjects who are progression free and the corresponding 95% CI will be estimated based on KM method at select timepoints (e.g., 6, 12, 18, 24, 30, 36 months, etc.) by treatment arm.

### 7.1.3 Sensitivity Analyses

The following sensitivity analyses will be performed for PFS as assessed by IRC between acalabrutinib and ibrutinib in support of primary efficacy analyses:

- Unstratified analyses
- The PFS will be analyzed as the time from date of randomization to the date of first IRC-assessed disease progression or death due to any cause, whichever comes first, regardless of the use of subsequent anticancer therapy; i.e., subjects will not be censored at the last adequate IRC assessment prior to the subsequent anticancer therapy
- Subjects with PFS events after 2 or more consecutively missed visits will not be censored at the last adequate assessment. In particular, IRC-confirmed progressive disease or death after 2 or more consecutively missed visits will be included as a PFS event
- Analysis using per protocol population

### 7.1.4 Subgroup Analyses

Subgroup analyses will be performed using potential prognostic variables at screening or baseline listed below to investigate the consistency and robustness of the primary analysis:

- Randomization stratification factors per IWRS recording:
  - Presence of 17p deletion mutation (yes vs. no)
  - ECOG at randomization (0, 1 vs. 2)
  - Number of prior therapies (1-3 vs.  $\geq 4$ ; additionally, analyze 1, 2, 3, 4,  $\geq 5$  separately)
- Region (North America, Western Europe, Central and Eastern Europe, Asia Pacific)
- Age group ( <65 vs.  $\geq 65$  years; <70 vs.  $\geq 70$  years; <75 vs.  $\geq 75$  years)
- Sex (male vs. female)
- Race (White vs. Non-White)
- Bulky disease (longest diameter of lymph node <5 cm vs.  $\geq 5$  cm or <10 cm vs.  $\geq 10$  cm at baseline)
- Rai Stage at screening (Stage 0-II vs. III-IV)
- Cytopenias at baseline (yes vs. no)

- Presence of 11q deletion mutation (yes vs. no)
- TP53 mutation (mutated vs. unmutated)
- IGHV (mutated vs. unmutated)
- Complex karyotype (yes vs. no)
- $\beta_2$ -microglobulin at baseline ( $\leq 3.5$  mg/L vs.  $> 3.5$  mg/L)
- High risk features:
  - 17p del and 11q del (yes, no)
  - 17p del and/or TP53 mutation (yes, no)
  - 17p del and TP53 mutation (yes, no)
  - 17p del and 11q del and TP53 mutation (yes, no)
  - 17p del and unmutated IGHV (yes, no)
  - 17p del and complex karyotype (yes, no)
  - 11q del and complex karyotype (yes, no)

The hazard ratio (Arm A/Arm B) and its corresponding 95% CI for each subgroup will be calculated based on an unstratified Cox regression model and displayed graphically in a forest plot.

Additional subgroups may be considered when appropriate.

## **7.2 Secondary Endpoints and Analyses**

### **7.2.1 Grade $\geq 3$ Infections, Richter's Transformation, and Atrial Fibrillation**

Secondary endpoints related to safety will be analyzed using the safety population, and subjects will be analyzed as treated. If a subject incorrectly received both acalabrutinib and ibrutinib in any amount, the subject will be analyzed under the acalabrutinib arm.

The incidences of treatment emergent grade  $\geq 3$  infections, Richter's transformation, and atrial fibrillation will be summarized and compared between the 2 treatment arms using 2-sided Cochran-Mantel-Haenszel tests adjusted for the randomization strata (same strata used for the primary analysis of PFS based on the pre-specified pooling strategy).

Richter's transformation will be assessed by central pathology. Incidence of grade  $\geq 3$  infections and atrial fibrillation will be collected as described for all AEs and defined according to Appendix 1.

In addition, subgroup analyses will be performed for each endpoint using the subgroups listed in Section 7.1.4. For each endpoint, the risk difference (Arm A – Arm B) and its

corresponding 95% CI for each subgroup will be calculated based on normal approximation (with use of Wilson's score) and displayed graphically in a forest plot.

### 7.2.2 Overall Survival

OS will be analyzed using the ITT population and is defined as the time from date of randomization to date of death due to any cause. Subjects who were not known to have died prior to the analysis data cutoff date will be right-censored as follows:

**Table 3.** Overall Survival Censoring

Situation	Date of Event or Censoring	Outcome
Death before first disease assessment	Date of death	Event
Death between scheduled assessments	Date of death	Event
All other cases will be censored as follows:		
Lost to follow-up immediately after randomization	Randomization date	Censored
Not known to have died at or prior to analysis data cutoff date	Date last known alive before analysis data cutoff date	Censored
Not known to have died prior to lost to follow-up or study exit	Date last known alive before lost to follow-up or study exit	Censored

OS will be calculated as death date (or censoring date) - randomization date + 1.

OS will be analyzed in the same fashion as that for primary efficacy endpoint as described in Section 7.1.2. A stratified log rank test will be performed, adjusting for the randomization stratification factors used for the primary analysis.

Additionally, a subgroup analysis will be performed for OS in the same manner, and using the same subgroups, as described in Section 7.1.4.

### 7.3 Exploratory Efficacy Endpoints and Analyses

CCI  
 [Redacted text block]

**7.3.1**

CCI [Redacted]

CCI [Redacted]

**7.3.2**

CCI [Redacted]

CCI [Redacted]

**7.3.3**

CCI [Redacted]

CCI [Redacted]

7.3.4

CCI [Redacted]

CCI [Redacted]

7.3.5

CCI [Redacted]

CCI [Redacted]

7.3.6

CCI [Redacted]

CCI [Redacted]

7.3.7

CCI [Redacted]

CCI [Redacted]

**7.3.8**CCI CCI **7.3.9 Additional Exploratory Analyses**

Additional exploratory analyses are described below. Further exploratory analyses may be conducted as appropriate.

**7.3.9.1**CCI CCI **8 SAFETY SUMMARIES**

All safety analyses will be performed using the safety population, and subjects will be analyzed as treated. If a subject incorrectly received both acalabrutinib and ibrutinib in any amount, the subject will be analyzed under the acalabrutinib arm.

Safety and tolerability will be assessed by the incidence of treatment emergent adverse events (TEAEs), changes in laboratory parameters and vital signs from baseline, and ECOG performance score.

## **8.1 Adverse Events**

Each adverse event terms recorded on the eCRF will be mapped to a preferred term and system organ class through use of the MedDRA. The severity of AEs will be graded using National Cancer Institute (NCI) Common Terminology Criteria for Adverse Events (CTCAE) v4.03 or higher for hematologic and non-hematologic AEs. The investigator will judge each event to be “not related” or “related” to study treatment.

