- An aggregate analysis of specific events that can be anticipated to occur in the study population independent of drug exposure. Such events include known consequences of the underlying disease or condition under investigation (eg, symptoms or disease progression), or events unlikely to be related to the underlying disease or condition under investigation, but commonly occur in the study population independent of drug therapy (eg, cardiovascular events in an elderly population). An aggregate analysis (across studies) will identify those events that occur more frequently in the drug treatment group than in a concurrent or historical control group.

This definition of “suspected adverse reaction” and the application of the “reasonable possibility” causality standard is considered to be consistent with the concepts and discussion about causality in the ICH E2A guidance ([FDA Guidance for Industry 1995](#)).

Severity

Definitions found in the Common Terminology Criteria for Adverse Events (CTCAE) version 4.03 or higher will be used for grading the severity (intensity) of nonhematologic AEs. The CTCAE v4.03 displays Grades 1 through 5 with unique clinical descriptions of severity for each referenced AE. Should a subject experience any AE not listed in the CTCAE v4.03 or higher, the following grading system should be used to assess severity:

- Grade 1 (Mild AE) – experiences which are usually transient, requiring no special treatment, and not interfering with the subject’s daily activities
- Grade 2 (Moderate AE) – experiences which introduce some level of inconvenience or concern to the subject, and which may interfere with daily activities, but are usually ameliorated by simple therapeutic measures
- Grade 3 (Severe AE) – experiences which are unacceptable or intolerable, significantly interrupt the subject’s usual daily activity, and require systemic drug therapy or other treatment
- Grade 4 (Life-threatening or disabling AE) – experiences which cause the subject to be in imminent danger of death
- Grade 5 (Death related to AE) – experiences which result in subject death

The grading scale for hematologic toxicity in subjects with CLL is provided in Appendix E.

Causality

The causality of AEs to the study drug will be assessed by means of the question: ‘Is there a reasonable possibility that the event may have been caused by the study drug?’ per FDA guidance on safety reporting requirements ([FDA Guidance 2012](#)).

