9.7 SAFETY ANALYSES

Safety data will be summarized for the safety population. The baseline value for safety analysis is defined as the value collected at the time closest to and before the start of study drug administration.

Adverse Events

AEs will be graded by the investigator according to the National Cancer Institute (NCI) CTCAE v4.03 or higher for non-hematologic AEs. Hematologic toxicity will be assessed by the grading scale for hematologic toxicity in CLL studies in the IWCLL 2008 guidelines. Each AE verbatim term will be coded to a system organ class and a preferred term using the Medical Dictionary for Regulatory Activities (MedDRA).

Treatment-emergent Adverse Events

All TEAEs will be summarized by treatment arm as treated. In addition, AE incidence rates will also be summarized by severity and relationship to study drug.

Grade 3 or Grade 4 TEAEs; TEAEs leading to permanent study drug treatment discontinuation; TEAEs leading to dose reduction; serious TEAEs; TEAEs of special interest and TEAEs resulting in death will be summarized by treatment arm as treated.

Clinical Laboratory Tests

Data Summary Methods:

For gradable parameters, a summary of worst post baseline toxicity grade will be provided in the treatment-emergent period and worst toxicity grade (any grade and Grade 3/4). The difference between groups in percentages will be displayed.

Liver function abnormality by Hy's law and frequencies of abnormal treatment emergent uric acid will be summarized.

Analysis of Lymphocytosis:

For all subjects with baseline and any post-baseline ALC measurements, ALC at peak summary will be provided by treatment arm. *Median percentage change in ALC from baseline with its 95% CI will also be displayed graphically over time.*

CCI [Redacted]
[Redacted]
[Redacted] CCI [Redacted]
[Redacted]

CCI [Redacted]
[Redacted]
[Redacted]
[Redacted]
[Redacted]
[Redacted]
[Redacted]

CCI [Redacted]
[Redacted]
[Redacted]
[Redacted]
[Redacted]

ECOG Performance Status

ECOG performance status will be collected as scheduled in [Appendix A](#). ECOG performance status grade ranges from 0 to 5. Descriptive statistics will be provided for each visit over time.

Vital Signs and Weight

Body temperature, heart rate (beats/min), systolic blood pressure (mmHg), diastolic blood pressure (mmHg), respiratory rate (breaths/min), and weight will be collected as scheduled in [Appendix A](#). For each parameter, descriptive statistics will be provided over time.

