### **8.1.1 Treatment Emergent Adverse Events**

TEAE is defined as an adverse event reported during the treatment emergent period (defined in Section 4.1.6). Any ongoing event that worsens in severity after the first dose date of study drug is also defined as a TEAE. Incomplete onset dates will be imputed as detailed in Section 4.2, for the purpose of determining whether AEs are treatment emergent.

TEAEs will be tabulated in summary tables by treatment arm. For each treatment arm, frequency and percentage of adverse events within each system organ class and preferred term will be presented. The denominator for the adverse event incidence will be based on the number of safety population subjects in that treatment arm, unless otherwise specified. Adverse event incidence rates will also be summarized by severity and relationship to study drug based on the investigator’s judgment.

Subjects with multiple occurrences of events for a given preferred term, system organ class, or overall will be counted only once at the maximum severity and strongest relationship to study drug, respectively, for each preferred term and system organ class.

In addition, Grade 3 or Grade 4 TEAEs, TEAEs that led to permanent study drug discontinuation, TEAEs that led to dose reduction, TEAEs that led to dose interruption, serious TEAEs, and TEAEs that resulted in death will be summarized by treatment arm as treated.

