### **8.1.4 Subgroup Analyses for Adverse Events**

Subgroup analyses will be performed for TEAEs using the same subgroups used for the primary endpoint subgroup analyses (listed in Section 7.1.4) to investigate benefit:risk for acalabrutinib versus ibrutinib.

For each of the TEAE types listed below, the risk difference (Arm A – Arm B) and its corresponding 95% CI for each subgroup will be calculated based on normal approximation (with use of Wilson's score) and displayed graphically in a forest plot. Additional subgroups may be considered as appropriate.

- Grade  $\geq 3$  TEAEs
- TEAEs leading to dose interruption
- TEAEs leading to discontinuation of treatment

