## **8.3 Laboratory Assessments**

### **8.3.1 Data Processing Methods**

All laboratory values will be converted to and reported as SI units and classified as normal, low, or high based on the normal ranges provided by the central laboratory. In general, only data from the central laboratory will be summarized and analyzed. Hematologic parameters, including platelet counts, hemoglobin, and neutrophils, will be assessed by the grading scale for hematologic toxicity in CLL studies with use of both the IWCLL 2008 guidelines and NCI CTCAE v4.03. All other gradable laboratory parameters will be graded using the NCI CTCAE v4.03.

Per the grading scale in the IWCLL guidelines, 1) ANC: Both baseline grade and post-baseline grade are defined based on absolute values, and (2) hemoglobin and

platelet: baseline grade is not applicable (no criterion is provided to define baseline grade), and post-baseline grade is based on percentage decrease from baseline value.

Gradable parameters that have criteria available for both low and high values (e.g., hypercalcemia for a high value of calcium and hypocalcemia for a low value of calcium) based on the NCI CTCAE v4.03 will be summarized for both criteria (low and high).

Subjects will be counted only once for each criterion/direction. The same subject can be counted for both criteria if the subject has laboratory values that meet each criterion.

Subjects who meet the criteria for Grade 1 or higher for the high direction will be summarized under Grade 0 for summarization of the low direction and vice versa.

Change from baseline to post-baseline value will be calculated for each parameter.

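### SAP 8.1 names CTCAE for hematologic AEs where the protocol names the IWCLL 2008 scale, and the IWCLL laboratory rule in SAP 8.3.1 leaves out Appendix E conditions that change grades

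*SAP*

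**What the plan says.** **AE severity.** SAP 8.1 has AEs "graded using National Cancer Institute (NCI) Common Terminology Criteria for Adverse Events (CTCAE) v4.03 or higher for hematologic and non-hematologic AEs". SAP 8.1.1 then plans severity tables ("Adverse event incidence rates will also be summarized by severity") and a Grade 3 or 4 TEAE summary. SAP 8.1.4 plans subgroup risk differences ("For each of the TEAE types listed below"), with Grade ≥ 3 TEAEs among the types.

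The protocol divides the scales differently. In section 7.2.1, CTCAE "will be used for grading the severity (intensity) of nonhematologic AEs", and "The grading scale for hematologic toxicity in subjects with CLL is provided in Appendix E". Section 9.7, under its Adverse Events heading, says "AEs will be graded by the investigator according to the National Cancer Institute (NCI) CTCAE v4.03 or higher for non-hematologic AEs" and continues "Hematologic toxicity will be assessed by the grading scale for hematologic toxicity in CLL studies in the IWCLL 2008 guidelines". The title of Appendix E presents it as a grading scheme for hematologic adverse events, so it is not a laboratory-only tool.

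**Laboratory values.** SAP 8.3.1 grades platelets, hemoglobin and neutrophils on both IWCLL 2008 and CTCAE. For IWCLL it states that ANC baseline and post-baseline "grade are defined based on absolute values", and that hemoglobin and platelets are graded post-baseline on percentage fall from baseline. SAP 8.3.2 tabulates the incidence of these toxicities by arm and grade.

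Three Appendix E footnotes add conditions that SAP 8.3.1 does not mention:

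- Footnote 2: platelets must be below normal for Grades 1 to 4. A count below 20,000/µL is Grade 4 whatever the fall, unless the count was already that low before treatment, in which case the subject is not evaluable for platelets.
- Footnote 3: hemoglobin must be below normal for Grades 1 to 4.
- Footnote 4: a subject with ANC below 1000/µL before therapy is not evaluable for ANC toxicity.

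**The concern.** Two documents that should agree give different scales for the same AE grades. A reader of the severity, Grade 3/4 and Grade ≥ 3 TEAE outputs would take cytopenia grades to be CTCAE grades when investigators were told to use Appendix E. No unredacted item in the SAP revision history records or justifies a change of scale. The IWCLL grading in SAP 8.3 concerns laboratory values only, so it does not settle which scale the AE tables carry.

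The laboratory part matters for a different reason. Appendix E exists because many of these subjects have cytopenias before any treatment. If its footnotes are left out, pre-existing neutropenia can appear as toxicity and some very low platelet counts can be under-graded. Safety and tolerability, including laboratory assessments, is a stated study objective, and these tables report on it.

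**Working it through.** The plan states no figure to reproduce here. The check sets the rules side by side and applies both to example values.

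**1. AE scale**

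| Type of AE | Protocol 7.2.1 and 9.7 | SAP 8.1 |
|---|---|---|
| Non-hematologic | CTCAE | CTCAE |
| Hematologic | IWCLL 2008 (Appendix E) | CTCAE |

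The second row conflicts. The documents give no CTCAE cut-offs, so no shift in grades between the scales can be calculated from them.

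**2. ANC**

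Inputs: inclusion criterion 8a admits ANC ≥ 750/µL, or ≥ 500/µL with documented marrow involvement. In Appendix E, Grade 3 is 500 to < 1000/µL and Grade 4 is < 500/µL.

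Take a subject at 800/µL before treatment and throughout. By the SAP 8.3.1 text, the baseline grade is 3 and the post-baseline grade is 3, so the subject can be counted at Grade 3 in the incidence table. By footnote 4, the subject is not evaluable.

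The share of such subjects is not in the documents. As a bound only, let f be the share of an arm with baseline ANC below 1000/µL, and r the Grade ≥ 3 rate in evaluable subjects. Suppose all of the share f count as Grade ≥ 3.

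- Rate by the SAP text: f + (1 − f) × r
- Rate by Appendix E: r
- Difference: f × (1 − r)

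For an assumed f of 2% to 10%, the difference is at most 2 to 10 points at r = 0, and 1 to 5 points at r = 50%.

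**3. Platelets**

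Fall = 100 × (1 − count / baseline). The Appendix E bands are 11–24% (Grade 1), 25–49% (Grade 2), 50–74% (Grade 3) and ≥ 75% (Grade 4).

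| Baseline/µL | Later count/µL | Fall | Grade, percentage only | Grade, footnote 2 |
|---|---|---|---|---|
| 25,000 | 19,000 | 24.0% | 1 | 4 |
| 30,000 | 19,000 | 36.7% | 2 | 4 |
| 60,000 | 19,000 | 68.3% | 3 | 4 |
| 80,000 | 19,000 | 76.3% | 4 | 4 |

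The upper limit of the mismatch is 20,000 / 0.25 = 80,000/µL: from there up, any count below 20,000/µL is already a fall of more than 75%. Likewise 20,000 / 0.50 = 40,000/µL, so Grade ≥ 3 status can change only for baselines below 40,000/µL. Between 40,000 and 80,000/µL the difference is Grade 3 against Grade 4.

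The lower limit is 20,000/µL. Inclusion criterion 8b sets a floor of 30,000/µL, but at screening. SAP 4.1.1 takes the last value before first dose as baseline, and that value may be lower. Below 20,000/µL before treatment, footnote 2 makes the subject not evaluable.

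**4. Below-normal condition**

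On percentage fall alone, a platelet count or hemoglobin that drops by 11% or more but stays within the normal range receives a grade. Footnotes 2 and 3 do not allow Grades 1 to 4 there. SAP 8.3.1 already classifies each value against central laboratory ranges, so the condition can be applied.

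**The case against.** The best defence of SAP 8.3.1 is that it invokes the IWCLL 2008 scale by name, so the footnotes come with it. On that view the disputed sentence only explains which parameters have a baseline grade. This is possible, and it is why the laboratory effect is stated as what could happen if the tables are programmed from the text. It does not remove the point: the SAP announces the IWCLL rule and then spells it out without the conditions, and the result differs for subjects the protocol can enrol.

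Several stronger readings are tempting and are not supported:

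- *Grade ≥ 3 TEAE rates or the subgroup forest plot would change.* The SAP describes no regrading of investigator-assigned grades, so no subject's status moves. Only the label is shown to be wrong.
- *SAP 8.3.2 confirms the ANC problem because it defines treatment-emergent abnormalities by timing, with no worsening condition.* That definition serves the CTCAE laboratory summary. The IWCLL incidence table is described in a separate paragraph that does not use it.
- *Hematologic AEs outside platelets, hemoglobin and ANC belong on CTCAE.* The protocol makes no such split, and footnote 4 says other white-cell decreases are not considered. The sponsor has to state what was used.
- *The ANC bound measures a real effect.* Both f and r are assumed; it only limits how large the effect could be.

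**Conclusion.** Both parts are wrong as written, and the point is minor.

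The AE scale conflict is plain from the text. Its demonstrated consequence is a wrong scale description on the severity, Grade 3/4 and Grade ≥ 3 TEAE outputs, with no claim about rates.

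The laboratory departure from Appendix E holds if SAP 8.3.1 is applied as stated. Unchanged baseline neutropenia could appear as Grade 3 in the IWCLL incidence table. Platelet counts below 20,000/µL from baselines of 20,000 to < 80,000/µL can fall below Grade 4. Platelet and hemoglobin values within normal limits can be graded. How many subjects this concerns cannot be determined from the documents.

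A reader might infer that the trial's formal conclusions are exposed. They are not: PFS, atrial fibrillation, Grade ≥ 3 infections, Richter's transformation and OS do not rest on platelet, hemoglobin or neutrophil grades.

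**What to change.** **SAP 8.1.** Reconcile the grading sentence with protocol 7.2.1 and 9.7. Name the scale actually used in the footnotes of the severity, Grade 3/4 and Grade ≥ 3 TEAE outputs. For hematologic AEs outside platelets, hemoglobin and ANC, have the sponsor state which scale was used.

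**SAP 8.3.1–8.3.2, IWCLL grades only:**

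- Exclude subjects with baseline ANC below 1000/µL from the numerator and denominator of the ANC table, and report how many by arm. The baseline IWCLL ANC grade of 3 or more, which the SAP already derives, identifies exactly this group.
- Treat subjects with pretreatment platelets below 20,000/µL as not evaluable for platelets, and grade other counts below 20,000/µL as Grade 4.
- Require a below-normal value for platelet and hemoglobin Grades 1 to 4.

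The CTCAE laboratory tables stay as they are and still show the excluded subjects. The cost is SAP wording, table footnotes, a denominator flag from an existing variable and a few programming rules, with no new data collection.
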